8.3 Analysis of Patient Reported Outcomes (PROs)

8.3.1 NRS Pain Data

The observed values and the derived change from baseline values will be listed and summarized descriptively for the following NRS knee pain variables:

- Overall of pain severity in the target knee last week (SDTM: Overall pain severity in target knee)
- Worst pain severity in target knee (SDTM: Worst pain severity in target knee)
- Overall pain severity in other knee (SDTM: Overall pain severity in other knee)
- Global Disease Activity (SDTM: How active was target knee arthritis)
- Satisfaction with target knee function (SDTM: How satisfied are you with target knee function)

8.3.1.1 Statistical Analysis of the NRS Pain Data

The statistical analysis of NRS Pain data will be performed using the same statistical analysis as for the Imorphics MRI described in in section 8.1.1. The output of the statistical analysis will be similar (see example figures and table section 8.1.1.) but will be based on the visits when the NRS assessments were conducted.

8.3.2 Intermittent and Constant Osteoarthritis Pain (ICOAP) Knee Version

The observed values and the derived change from baseline values will be listed for the three transformed ICOAP scores (Constant Pain, Intermittent Pain, and Total Pain). The transformed ICOAP will take values between 0 and 100 and will be calculated as follows:

Constant pain subscale

To calculate the Total constant pain subscale, sum the scores within each time point for items IP1 through IP5. Maximum constant pain score ranges from 0 to 20.

This score can be transformed to a score out of 100 using the following formula:

$(\text{Total constant pain score} / 20) \times 100$

Intermittent pain subscale

To calculate the total intermittent pain subscale, sum the scores within each time point for items IP6 through IP11. Maximum intermittent pain subscale ranges from 0 to 24.

This score can be transformed to a score out of 100 using the following formula:

$(\text{Total intermittent pain score} / 24) \times 100$

PAREXEL International Statistical Analysis Plan

Medivir
Protocol: MIV-711-202

Final 1.0
16 January 2018

Total pain score

To calculate the total ICOAP score, sum the constant and intermittent pain subscales within each time point. Maximum total pain score ranges from 0 to 44.

This score can be transformed to a score out of 100 using the following formula:

$(\text{Total pain score} / 44) \times 100$

8.3.3 Analysis of WOMAC

Normalized WOMAC scores, taking scores between 0 and 100, will be derived for each of the three WOMAC domains: WOMAC pain, WOMAC function, and WOMAC stiffness as follows:

For each subject and each scheduled time point derive the total WOMAC score for each of the three domains:

- Total WOMAC Pain Score (Total_WOMAC_Pain_50) = Sum of the five WOMAC pain item scores. Denote this new variable in the data set as 'WOMAC_Pain_50'.
- Total WOMAC Function Score (Total_WOMAC_Func_170) = Sum of all 17 WOMAC difficulty item scores. Denote this new variable in the data set as 'WOMAC_Func_170'
- Total WOMAC Stiffness Score (Total_WOMAC_Stiff_20) = Sum of the 2 WOMAC stiffness item scores. Denote this new variable in the data set as 'WOMAC_Stiff_20'.

Each of the total WOMAC scores will be normalized using the following multipliers:

- Normalized WOMAC PAIN Score = Total_WOMAC_Pain_50 x 2.
- Normalized WOMAC Function Score = Total_WOMAC_Func_170 ÷ 1.7.
- Normalized WOMAC stiffness Score = Total_WOMAC_Stiff_20 x 5.

8.3.3.1 Statistical analysis of WOMAC

The statistical analysis of the three normalized WOMAC scores will be performed using the same statistical analysis as for the Imorphics MRI described in section 8.1.1. An additional linear model will be included for the individual WOMAC Pain score WOMAC1-Pain - walking on a flat surface. The output from these statistical analysis will be similar to that for the imorphics and NRS data (see example figures and table section 8.1.1.), except the analysis will be based on the visits when the WOMAC assessments were conducted.

PAREXEL International Statistical Analysis Plan

Medivir
Protocol: MIV-711-202

Final 1.0
16 January 2018

8.3.4 (OARSI)-OMERACT Responder Criteria

The OARSI-OMERACT response (Yes, No) will be derived from the PROs from the WOMAC scores (the Normalized WOMAC PAIN Score and the Normalized WOMAC Function Score as defined in section 8.3.3 and the Patient Global Assessment (NRS question 4: Over the past week, how active do you think your knee arthritis has been?).

The OARSI-OMERACT response (Yes, No) will be calculated for visit 5 MIV-711-202 for each patient by the following steps:

Step 1. Normalize the Patient Global Assessment score so it takes values between 0 and 100 in the same way as the Normalized WOMAC PAIN Score and the Normalized WOMAC Function Score described in section 8.3.3:

- a) Normalized Global Assessment Score:
$$\text{NRSACT}_{100} = (\text{Global Assessment Score}) \times 10.$$

Step 2. Use the normalized scores to derive change from baseline and percentage change from baseline for visit 5 MIV-711-202:

Denote the change from baseline scores as:

- CHG_WOMAC_PAIN_100
- CHG_WOMAC_FUNC_100
- CHG_NRSACT_100

Denote the percentage change from baseline scores as:

- PCHG_WOMAC_PAIN_100
- PCHG_WOMAC_FUNC_100
- PCHG_NRSACT_100

Percentage change from baseline will be calculated as:
$$((\text{Visit 5 Score} - \text{baseline Score}) \div \text{aseline Score}) \times 100$$

Step 3. Derive Responder OARSI-OMERACT (Yes, No): In assessing for a positive OMERACT response, patient improvement (Response = Yes) is associated with decreases (negative changes) from baseline and (negative) percentage (changes) decreases from baseline. The different criteria are quantified in the tables below.

Case 1: using the change from baseline and percentage change from baseline scores for WOMAC pain and WOMAC function (from step 2), an OMERACT responder will be flagged as 'Yes' if either of the following 2 criteria are satisfied:

PAREXEL International Statistical Analysis Plan

Medivir
Protocol: MIV-711-202

Final 1.0
16 January 2018

Criteria		Decrease from Baseline		Percentage Decrease from Baseline	OMERACT Responder
1	WOMAC Pain	≥ 20	and	$\geq 50\%$	Yes
2	WOMAC Function	≥ 20	and	$\geq 50\%$	Yes

Case 2: using the change from baseline and percentage change from baseline scores for WOMAC pain, WOMAC function, and global assessment score (from step 2), an OMERACT responder will be flagged as ‘Yes’ if at least 2 of the following 3 criteria are satisfied:

Criteria		Decrease from Baseline		Percentage Decrease from Baseline	OMERACT Responder
3	WOMAC Pain	≥ 10	and	$\geq 20\%$	Yes
4	WOMAC Function	≥ 10	and	$\geq 20\%$	Yes
5	Global Assessment NRS	≥ 10	and	$\geq 20\%$	Yes

A subject is a ‘Yes’ responder if either of criteria 1 or 2 are satisfied. If neither criteria 1 or 2 are satisfied, criteria 3, 4 and 5 will be checked.

A listing will be created that presents each patient’s responder status by visit. Included in this listing will be the associated change from baseline and percent change from baseline values.

8.3.5 Global Improvements

Global improvements in knee problem, knee pain and knee function that were recorded on a 6-point Likert scale: completely better, much better, better, no change, worse, much worse. All data will be listed for each patient.

8.3.6 Quality of Life PRO – EQ-5D-5L

The observed values and the derived change from baseline values for the six items of Quality of Life PRO – EQ-5D-5L described in section 4.5.3.6 will be listed and summarized descriptively.

PAREXEL International Statistical Analysis Plan

Medivir
Protocol: MIV-711-202

Final 1.0
16 January 2018

8.3.7 E-diary for Patient Pain

All data collected in e-diary format will be listed for each patient.

The observed values and the change from baseline values for the derived e-diary summary scores described in section 8.3.7.1 below will be listed and summarized descriptively.

8.3.7.1 Derived e-diary variables

Three e-diary variables will be derived:

- NRS score
- Percentage score for analgesic usage last 12 hours
- Severity and extent of their pain medication usage

For each e-diary endpoint and visit, a patient's summary value will be calculated by using the e-diary assessments recorded at the study days associated with that study visit. The study days associated with study Visit 'x' will be identified as follows: beginning at the last date of assessment associated with Visit 'x' and including up to 14 days prior to the visit recorded within 19 calendar days prior to the date of Visit 'x'. If there are less than 10 days of recorded e-diary assessment within those 19 calendar days, the summary value will not be calculated for that visit.

NRS score

The derived summary scores for e-diary NRS scores associated with each visit will be obtained as the arithmetic mean (the average) of all e-diary NRS scores observed during the study days associated with that visit (as defined above). Separate e-diary NRS summary scores will be provided for AM and PM response. In addition, the overall 24 hour summary score will be calculated as the mean of the AM and PM summary scores for each visit. The overall 24 hour summary score will only be calculated if both mean AM and mean PM scores are available.

Percentage score for analgesic usage last 12 hours

Each patient's 'pain medication usage over the last 12 hours (Yes/No)' will be calculated as the percentages of days with a YES-response of the study days associated with that visit (as defined above). This will provide each patient with a percentage score for analgesic use for each study visit and for each of AM, PM. The denominator for AM and PM percentage calculations will be the actual number of days assessed, such that the number of days is at least 10 days and less than or equal to 14 days. The overall percentage, combining AM and PM measures, will be calculated as the mean of the AM and PM percentages:

- Overall percentage = $(xx/AM \text{ denominator} + yy/PM \text{ denominator})/2$
where 'xx' is the count of AM 'Yes' responses, 'yy' is the count of PM 'Yes' responses.

PAREXEL International Statistical Analysis Plan

Medivir
Protocol: MIV-711-202

Final 1.0
16 January 2018

Severity and extent of their pain medication usage

Each patient's summary score for severity and extent of their pain medication usage ('More than Normal', 'Normal', 'Less than normal') will be the worst (most severe) response recorded during the study days associated with each visit (as defined above). The summary score will only be calculated if the patient responded 'YES' to 'Pain medication Usage' within the study days associated with the actual visit (as defined above). Summaries will be provided by visit, with separate summary score for AM and PM. The overall 24 hour summary score will be the worst (most severe) of the AM and the PM summary score and will be calculated if the AM and the PM summary score are available.

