2.4 Exploratory Objectives Study Group A

Data from both MIV-711-201 and MIV-711-202 study will be used for Group A assessment.

In addition, the study will investigate the following exploratory parameters.

- The effect of MIV-711 on worst target knee pain (1 week recall)
- The effect of MIV-711 on average contralateral knee pain (1 week recall)
- The effect of MIV-711 on constant and intermittent OA pain
- The effect of MIV-711 on global improvements in knee problem, knee pain and knee function
- The effect of MIV-711 on knee joint OA symptoms (function, pain, stiffness)
- The effect of MIV-711 on global disease activity
- The effect of MIV-711 on quality of life (QoL)
- The effect of MIV-711 on patient reported e-diary daily recall knee joint pain
- The effect of MIV-711 on patient reported e-diary daily recall analgesics use
- Assessment of the effect of MIV-711 on exploratory serum and urinary biomarkers of relevance for OA including but not limited to procollagen type I N-terminal propeptide (PINP), bone specific alkaline phosphatase (BSAP), N-terminal telopeptide of collagen type I (NTX-I), CTX-I, aCTX-I, CTX-II and tartrate-resistant acid phosphatases (TRAP5b).
- Baseline and steady state treatment blood and urinary samples will be stored for patients who sign a separate voluntary Informed Consent Form (ICF) for potential future pharmacogenomics and disease-related proteomics, genomics, metabolomics and lipidomics analyses.
- The effect of MIV-711 on a compound index of MRI bone area and cartilage thickness
- The pharmacokinetics of MIV-711 and the relationship to patient actors and concomitant medications

PAREXEL International Statistical Analysis Plan

Medivir
Protocol: MIV-711-202

Final 1.0
16 January 2018

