4.5.3.8 E-Diary Assessment of NRS and Analgesic Use

In an e-diary format, a patient knee pain diary (NRS) and analgesia questionnaire will be completed daily every 12 hours (AM, PM) during two 2-week periods prior to visit 4 and visit 5. The assessments in the e-diary comprise:

PAREXEL International Statistical Analysis Plan

Medivir
Protocol: MIV-711-202

Final 1.0
16 January 2018

- Average overall knee pain severity in the target knee over the past 12 h (0 -10 NRS)
- Adherence to usual analgesics regimen:
 - Has patient taken any pain medication over last 12 hours? (Yes, No).
 - Classify your pain medication usage over the last 12 hours: (More than normal, Normal, Less than normal)
- Intake of IMP (note: the e-diary device is kept by the patients for the full duration of the study, intake of IMP will be registered daily throughout the study)

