16 January 2018

Medivir
Protocol Number: MIV-711-202

Page X of Y

Listing 16.2.6.20
Brief Medication Questionnaire

Study Group = Group A

Patient MIV-711- 202	Patient MIV- 711-201	Visit	Date Of Assessment	Question	Response
				How much did you take each time	
				How many days did you take it	
				The dosage times are inconvenient	
				Etc...	

PAREXEL International SAP Amendment Shells

Medivir
Protocol: MIV-711-202

Final 1.0
16 January 2018

Medivir
Protocol Number: MIV-711-202

Page X of Y

Listing 16.2.6.21
E-Diary Assessments over the Last 12 Hours

Study Group = Group A

Patient MIV-711- 202	Patient MIV- 711-201	Study Day	Date Of Assessment	Time Point	Pain Medication Use Over Last 12 Hours?	Severity Pain Medication Usage Over last 12 Hours	NRS: Overall Pain Severity in Target Knee Over Last 12 Hours
				AM			
				PM	YES	Less than Normal	
					NO	Normal	
						More than normal	

PAREXEL International SAP Amendment Shells

Medivir
Protocol: MIV-711-202

Final 1.0
16 January 2018

Medivir
Protocol Number: MIV-711-202

Page X of Y

Listing 16.2.6.22
E-Diary Assessments - Derived Results for each Study Visit

Study Group = Group A

Patient MIV-711- 202	Patient MIV-711-201	Visit	Time Point	Percentage of Patients who used Pain medication use over last 12 hours?	Change from Baseline percentage of 'Yes' scores for analgesic use	Severity Pain medication usage over last 12 hours [2]	NRS: Overall pain severity in target knee over last 12 hours [3]	Change from Baseline NRS
xxxxxx		Baseline	AM	xx.x				
		Visit 4	AM	xx.x	xx.x	Less than Normal		
		Visit 5	AM	xx.x	xx.x	Normal		
		Baseline	PM			More than normal		
		Visit 4	PM					
		Visit 5	PM					
		Baseline	Overall					
		Visit 4	Overall					
		Visit 5	Overall					

Baseline is defined as: Visit 2 in the MIV-711-201 for Group A, Visit 8 in the MIV-711-201 for Group B

[1] Denominator for AM, PM calculations is the actual number of days assessed, where the number of days ≥ 10 days and ≤ 14 days. The overall percentage combining AM and PM measures:

Overall percentage = $(xx/AM \text{ denominator} + yy/PM \text{ denominator})/2$, where 'xx' = count of AM 'Yes', 'yy' = count of PM 'Yes'.

[2] Derived results were considered only for YES responses in [1]. For those cases the worst response over the interval of all responses for each visit was interpreted as the derived response for that Visit.

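### The e-diary more/normal/less rating of analgesic use is summarised only by its worst value per visit, so no summary shows how often use was above or below the patient's normal

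*SAP*

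**What the plan says.** SAP section 2.4 lists among the exploratory objectives "The effect of MIV-711 on patient reported e-diary daily recall analgesics use". Section 4.5.3.8 describes the diary as "completed daily every 12 hours (AM, PM) during two 2-week periods prior to visit 4 and visit 5". It asks first whether any pain medication was taken (yes/no) and then "Classify your pain medication usage over the last 12 hours: (More than normal, Normal, Less than normal".

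Section 8.3.7.1 derives two analgesic variables from these answers.

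- **Yes/no item.** The visit value "will be calculated as the percentages of days with a YES-response of the study days associated with that visit (as defined above". It has AM, PM and overall versions, a change-from-baseline table (14.2.6.3) and figures over time (14.2.5.3 and 14.2.5.4).
- **More/normal/less item.** The visit value "will be the worst (most severe) response recorded during the study days associated with each visit (as defined above", separately for AM and PM. The 24-hour score is the worse of the two. A score is derived only when use was reported. Footnote [2] to Listing 16.2.6.22 limits the derivation to YES responses and adds: "For those cases the worst response over the interval of all responses for each visit was interpreted as the derived response for that Visit".

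The visit window is defined as "including up to 14 days prior to the visit recorded within 19 calendar days prior to the date of Visit 'x". No visit value is calculated "If there are less than 10 days of recorded e-diary assessment within those 19 calendar days". That minimum counts diary days, not more/normal/less ratings.

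**The concern.** A worst-of rule discards frequency. A single half-day of extra use puts the whole visit in the top category, and a patient reaches 'Less than normal' only if every contributing rating is 'Less'. Reduced use, the favourable direction, is therefore the hardest result to register. Because the score is a maximum, it also rises with the number of ratings, so differences in diary completion, or in how often analgesics are taken, can look like differences in the amount taken.

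This matters because patients may raise or lower their analgesic dose during the study (protocol sections 6.6.1 and 6.6.3), and in an open-label study without a control arm, analgesic use is part of reading the pain scores. A regular user who changes the dose still answers yes, so the yes/no percentage does not move. Among the derived e-diary scores, only the more/normal/less item could show that change, and the plan summarises it only by its extreme.

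**Working it through.** The plan states no figure for this score, so there is none to reproduce. The check is of how the rule behaves.

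**Inputs from the SAP (section 8.3.7.1 and Listing 16.2.6.22).** At most 14 AM and 14 PM ratings per visit, so at most 28 for the 24-hour score. At least 10 recorded diary days. Only YES half-days contribute, so the number of ratings n can be below 10.

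**Assumed inputs.** The documents give no response rates. Let p be the chance that a rating is 'More' and q the chance that it is 'Less'.

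**Step 1: independent ratings.** P(visit scored 'More than normal') = 1 − (1 − p)^n.

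| p | n = 7 | n = 10 | n = 14 | n = 28 |
|---|---|---|---|---|
| 0.02 | 13.2% | 18.3% | 24.6% | 43.2% |
| 0.05 | 30.2% | 40.1% | 51.2% | 76.2% |
| 0.10 | 52.2% | 65.1% | 77.1% | 94.8% |
| 0.20 | 79.0% | 89.3% | 95.6% | 99.8% |

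For example, 1 − 0.9^7 = 1 − 0.478 = 0.522 and 1 − 0.9^14 = 1 − 0.229 = 0.771. Along each row behaviour per rating is constant and only the number of ratings changes. A share of ratings has expectation p whatever n is.

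**Step 2: ratings clustered within patients.** Let patient rates follow a beta distribution with mean p and concentration c, so a = cp and b = c(1 − p). Then P(at least one 'More') = 1 − ∏ (b + i)/(c + i), for i = 0 to n − 1. With n = 14:

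| p | c = 2 | c = 20 | independent |
|---|---|---|---|
| 0.05 | 20.9% | 42.4% | 51.2% |
| 0.10 | 37.9% | 67.6% | 77.1% |
| 0.20 | 62.4% | 90.5% | 95.6% |

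**Step 3: response to a change, n = 14.** Halving p from 0.20 to 0.10 moves the score from 95.6% to 77.1% if independent (18.5 points). Under clustering it moves from 62.4% to 37.9% (24.5 points, c = 2) or from 90.5% to 67.6% (22.9 points, c = 20). Halving p from 0.10 to 0.05 moves it from 77.1% to 51.2% if independent (25.9 points). For the 24-hour score (n = 28, independent), 0.20 to 0.10 moves it only from 99.8% to 94.8% (5.0 points).

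**Step 4: the lower end.** P(visit scored 'Less than normal') = q^n if independent. With q = 0.7 and n = 14, 0.7^14 = 0.7%. With beta-distributed rates it is 22.0% (c = 2) or 2.4% (c = 20). A patient whose ratings are mostly 'Less' will usually not be scored 'Less' under these assumptions.

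**The case against.** The strongest reply is that the objective is already served. The yes/no percentage uses every recorded day and is reported as change from baseline. All diary entries are listed. The concomitant-medication tables and the Brief Medication Questionnaire also describe use. This stands for how often analgesics are taken. It does not cover how much is taken relative to normal: among the derived e-diary scores, only the worst-of score addresses that.

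A second reply is that protocol section 7.4.1 presents the item as adherence to the usual regimen, for which recording any excess in the window is defensible. That justifies keeping the worst-response table, but not making it the only summary.

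A reader might go further and infer that the score sits at its ceiling for most patients and so cannot show a change. The documents do not support that as a general statement. No rates are given, patients are asked to keep their usual regimen where possible, and at low rates or with clustering the AM and PM scores are well short of the ceiling and do move. A reader might also infer a loss of power. No test of this score is planned: the mixed model in SAP section 8.3.7.2 is assigned to the e-diary NRS, and protocol section 9.2.1 says the study is not powered for confirmatory analyses.

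**Conclusion.** The concern holds in a limited form. The worst-of rule discards frequency, depends on the number of ratings and makes 'Less than normal' hard to reach. The first and third follow from the rule itself, with no assumed rates. The sizes do rest on assumptions. At an assumed, independent 10% rate, going from 7 to 14 ratings raises the percentage scored 'More than normal' from 52.2% to 77.1% with no change in behaviour per rating. With 14 ratings, closeness to the ceiling runs from 62% to 96% at an assumed 20% rate and from 21% to 51% at 5%, depending on clustering.

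The gap is confined to the amount used relative to the patient's normal. It affects one exploratory, descriptive e-diary variable and no primary or secondary conclusion. It is worth considering because the remedy is cheap.

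**What to change.** In SAP section 8.3.7.1 add, per visit and for AM, PM and overall:

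- **(a)** the percentage of YES (rated) half-days scored 'More than normal' and the percentage scored 'Less than normal', reported with the number of rated half-days;
- **(b)** the percentage of all recorded half-days scored 'More than normal', counting NO half-days as not 'More'.

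Keep the existing minimum of 10 recorded days. Do not use recorded days as the denominator for 'Less': NO half-days carry no rating, so a patient who stopped analgesics would show 0% 'Less'. Summarise observed values and change from baseline as in Table 14.2.6.3, read them beside the yes/no percentage, and keep the worst-response table as a supplement.

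The cost is one more derivation and one more table, from data already collected. The shares in (a) will be imprecise for patients with few YES half-days and undefined for those with none, which is why the number of rated half-days should be shown.

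### The 24-hour pain-medication severity score is left missing for patients who never take analgesics in one half of the day, although their non-use is known

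*SAP*

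**What the plan says.** The e-diary is "completed daily every 12 hours (AM, PM) during two 2-week periods" before Visits 4 and 5 (SAP Section 4.5.3.8). Each entry asks whether pain medication was taken in the last 12 hours and, as a separate question, whether use was less than normal, normal or more than normal.

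SAP Section 8.3.7.1 reduces the second question to one severity value per visit, the worst response in the visit window:

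- **Condition on use:** "The summary score will only be calculated if the patient responded 'YES' to 'Pain medication Usage"; the answer must fall in the window for that visit.
- **Half-days:** results are given by visit, "with separate summary score for AM and PM".
- **Overall value:** the two half-day values are combined by taking the more severe one.
- **Condition on the overall value:** it "will be calculated if the AM and the PM summary score are available".

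Footnote [2] of the shell for Listing 16.2.6.22 adds: "Derived results were considered only for YES responses in [1", where [1] is the yes/no use item.

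The severity table is listed as Table 14.2.6.4 in SAP Section 11, and its shell is numbered 14.2.6.65. Its footnote defines the number of patients as those answering YES for each visit and group. A programming note extends the table from AM to PM and to the 24-hour assessment. SAP Section 6 allows no imputation, and no fallback is given for a patient with only one half-day score.

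**The concern.** A worst-of-two score needs both components only when an absent component might hide something worse. Here one component can be absent because the patient completed the diary and answered NO each time. That is a known state, yet the rule treats it like an incomplete diary.

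The result is an odd ordering. A patient with 'More than normal' every morning and no evening use has no 24-hour severity, while a patient with 'Less than normal' in both halves has one. A patient who stops evening analgesics between Visit 4 and Visit 5 leaves the 24-hour row, so its composition can shift between visits for reasons that are themselves part of the outcome.

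Analgesic use recorded by e-diary is a named exploratory objective (Protocol Section 3.4; SAP Section 2.4). Protocol Section 6.6.1 lets patients change analgesics during the study, and there is no control arm. A reader will use this table to judge whether a change in pain scores came with a change in medication.

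**Working it through.** There is no stated figure to reproduce. The check applies the written rule to every possible case.

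**1. Patterns.** Each half-day takes one of four states: no score (no YES in the window), Less, Normal or More. That gives 4 × 4 = 16 patterns, and 16 − 1 = 15 with some use.

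| | Patterns | Scored as written | Scored with worst-of-available |
|---|---|---|---|
| Any use | 15 | 3 × 3 = 9 | 15 |
| Containing 'More than normal' | 7 | 9 − 2 × 2 = 5 | 7 |

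As written, 15 − 9 = 6 patterns get no overall score. Two of them are More/none and none/More. These are counts of patterns, not of patients, because the patterns are not equally likely.

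**2. Comparison with the usage percentage.** Section 8.3.7.1 calculates the overall percentage as (AM YES count / AM days + PM YES count / PM days) / 2, with each denominator "such that the number of days is at least 10 days and less than or equal to 14 days". Take a patient with 14 completed days in each half, YES every morning and NO every evening. The overall percentage is (14/14 + 0/14)/2 = 50%. The same entries give no overall severity. One section thus treats the same non-use as a value in one variable and as a gap in the other.

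**3. Comparison with the table shell.** If the shell's patient count means anyone with a YES, one-half-day users are in the count but in no severity category, and the categories do not add up to it. If the count means patients with both scores, the footnote is wrong for the 24-hour row.

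**4. How strict the condition is.** The score is lost only if the other half has no YES in the whole window. If use in that half has daily probability q, independently across days (both are assumptions), the chance of no YES in n diary days is (1 − q)^n:

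| q (assumed) | n = 10 | n = 14 |
|---|---|---|
| 0 | 100% | 100% |
| 0.02 | 82% | 75% |
| 0.05 | 60% | 49% |
| 0.10 | 35% | 23% |
| 0.20 | 11% | 4% |
| 0.30 | 3% | 1% |

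The rule mainly removes patients who almost never medicate in one half. Occasional use, at 20% of days or more, usually creates the second score.

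**The case against.** **The text does not tie the YES condition to a half-day.** Section 8.3.7.1 asks for a YES within the visit's study days before it mentions AM and PM, so a single YES anywhere might open both scores. Section 4.5.3.8 states no skip rule between the two questions. This reading keeps the patient only if severity is recorded and used after a NO, and the footnote of Listing 16.2.6.22 limits the derivation to YES responses. The section still needs a clarifying sentence.

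**Requiring both halves has a rationale.** The same section requires both halves for the diary pain mean. It also guards against a 24-hour label on a patient who completed only morning entries: for severity, the 10-day completeness rule is not stated per half-day. This point stands, and the fix has to respect it.

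**Little is lost.** The patient's responses stay in the AM or PM rows and in Listings 16.2.6.21 and 16.2.6.22, and the patient keeps an overall usage percentage. SAP Section 8.3.7.2 specifies the mixed model for the diary pain score, not for severity. Protocol Section 9.2.1 says the study is not powered for confirmatory analysis. This also stands.

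**Stronger readings.** A reader might infer that every patient who usually medicates in one half is lost, or that the 24-hour denominator falls by a definite share such as 20% to 40%. The documents support neither. The loss needs no YES at all in the other half over the window. No usage pattern is given, so any percentage only restates its own assumption. The shell's footnote would in fact keep these patients in the count.

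**Conclusion.** The rule is wrong as written, at a minor level. It leaves a worst-of score missing when one component is absent through known non-use, and it disagrees both with the usage percentage in the same section and with the table's patient count.

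This rests on reading the YES condition together with the listing footnote, so that a half-day with no YES has no severity score. That is the most natural reading, but it is not spelled out.

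The number of patients affected cannot be stated. The 24-hour row can be selected towards patients who medicate in both halves of the day. A reader might go further and call them heavier users overall, which is plausible but not shown. The effect is confined to one row of an exploratory descriptive table. The separate AM and PM rows and the primary safety endpoint are not affected.

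**What to change.** In SAP Section 8.3.7.1:

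- Define the 24-hour severity score as the worst of the available AM and PM scores, calculated when at least one exists and the diary was completed on at least 10 days in each half-day.
- State that a half-day with enough completed entries and no YES is 'no use', and that one with fewer than 10 completed days is 'diary missing'. Only the second blocks the overall score.
- State that the YES condition applies separately to AM and to PM.

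In the severity table shell, change the patient-count footnote to match: for AM and PM, patients with a score in that half; for 24 hours, patients with an overall score under this rule.

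For patients with adequate diaries, all 15 patterns of use are then classified and all 7 containing 'More than normal' are shown as such. The cost is a sentence or two in the SAP, one footnote and a small programming change. No new data are needed.
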